This Statistical Analysis Plan (SAP) describes the planned analyses for the NeuroNEXT NN102 (SPRINT-MS) study [National Institute of Neurological Disorders and Stroke (NINDS) grant # U01NS082329]. The planned analyses identified in this SAP are intended to support the completion of the Final Study Report (FSR) and will be included in regulatory submissions and/or future manuscripts. All interim analyses will involve only the primary study endpoint, and will be performed once the specified number of randomized subjects have completed the full study period. All final, planned analyses identified in this SAP will be performed only after the last randomized subject has completed the full study period. Once all data have been cleaned and verified, a “locked” version of the data will be used for reporting the final study results. Key statistics and study results will be made available to the Protocol Principal Investigator (PPI) following database lock and prior to completion of the final FSR.

1. STUDY DESIGN

This is a multicenter, phase II, randomized, double-blind, placebo controlled, parallel group study designed to generate proof-of-concept evidence to evaluate the activity of Ibudilast (MN-166) on imaging measures of brain atrophy and tissue integrity, to evaluate the safety and tolerability of Ibudilast over two years, and to identify imaging markers for measuring biologic activities of potential therapies in progressive MS. A total of 250 male and female subjects from 21 to 65 years old, inclusive, will be enrolled into two treatment groups across sites within the NeuroNEXT network. Subjects will be randomized in a 1:1 fashion to receive either Ibudilast (100 mg/day; n = 125) or matching placebo (n = 125). Randomization of subjects will be stratified by disease status [primary progressive MS (PPMS) or secondary progressive MS (SPMS)] and immunomodulation therapy [untreated with long-term MS disease modifying therapy or receiving either glatiramer acetate (GA) or interferon beta (IFN β -1a: Avonex, Rebix or IFN β -1b: Betaseron, Etavia) treatment]. Study drug will be administered either two times per day (i.e., MN-166 50 mg or placebo taken in the morning and evening) or three times per day, depending on subject’s tolerance to study drug. The study will consist of a screening phase (up to 45 days), followed by a treatment phase (96 weeks), and a follow-up visit (1 month post week 96 visit). Thus, subjects will be involved for approximately 100 weeks in the various phases of the study.

During the screening phase, subjects will be assessed for study eligibility. The baseline visit must occur within 45 days following the screening visit. At the baseline visit (day 1), subjects who have completed all of the screening assessments and continue to meet eligibility criteria will be randomized to one of two treatment groups and will take 3 capsules of study medication on the evening of day 1. On the morning of day 2, all subjects will begin a three capsule BID (twice daily) dosing regimen through day 14. Subjects randomized to MN-166 will start at 60 mg/day (30 mg BID) and will remain on 60 mg/day through day 14. Beginning on day 15, all subjects will begin a 5 capsule BID regimen; those randomized to MN-166 will therefore be taking 100 mg/day (50 mg BID). After day 15, subjects with intolerable side effects (e.g., nausea, diarrhea, vertigo) may reduce their dose to either 4 capsules twice a day (80 mg/day for those taking MN-166) or 3 capsules twice a day (60 mg/day for those taking MN-166). Subjects with intolerable side effects at the end of day 14 may continue taking 3 capsules twice a day at the Investigator’s discretion. At the Investigator’s discretion, the daily dose of Ibudilast can be changed between 3 capsules twice a day, 4 capsules twice a day, and 5 capsules twice a day over the first 8 weeks of treatment. At the end of the first 8 weeks of treatment, the subject must maintain their then-current daily dose of study medication (3 capsules twice per day, 4 capsules twice per day, or 5 capsules twice per day) for the duration of the trial. Additionally, at the

Investigator's discretion, the daily dose of Ibudilast may be divided and taken three times per day to improve tolerability. Subjects will return to the clinic for follow-up visits on a regular basis at weeks 4, 8, 12, 24, 36, 48, 60, 72, and 96. All subjects who complete the study on drug will return for a follow-up safety visit at week 100 (4 weeks after their last study visit) to assess general health and adverse event status.

Subjects who experience a relapse will return to the clinic within three days of notifying the Investigator, and will undergo assessments as described in Table 2 (Schedule of Unplanned Procedures and Assessments) of the study protocol.

Subjects who prematurely discontinue study medication will continue to be followed on a semi-annual basis until the end of the study. For such subjects, adverse events will not be collected post study drug discontinuation. Existing AEs will be followed until the AE resolves or stabilizes.

1.1 Primary Objectives

Primary Objective #1: Evaluate the activity of Ibudilast (MN-166: 100 mg/day) versus placebo at 96 weeks as measured by quantitative MRI analysis for whole brain atrophy using brain parenchymal fraction (BPF).

Primary Objective #2: Evaluate the safety and tolerability of Ibudilast (MN-166) versus placebo

1.2 Major Secondary Objectives

Major Secondary Objective: Evaluate the activity of Ibudilast (MN-166) versus placebo as measured by:

- (1) Diffusion tensor imaging (DTI) in descending pyramidal white matter tracts
- (2) Magnetization transfer ratio (MTR) imaging in normal-appearing brain tissue
- (3) Retinal nerve fiber layer thickness as measured by Optical coherence tomography (OCT)
- (4) Cortical atrophy as measured by cortical longitudinal atrophy detection algorithm (CLADA)

Brain MRI will be performed in a standard fashion, as outlined in the MRI procedure manual. Each subject's baseline MRI must be approved by the MRI Reading Center prior to randomization. All sites will perform a test (or "dummy") MRI scan prior to study initiation. This test MRI will ensure adequate performance of the study MRI. It is required that the same MRI scanner be used to acquire all MRI scans over the course of the study. If during the study period a study site needs to change the MRI scanner or the current MRI scanner undergoes significant upgrades (hardware or software), the investigator should notify the Clinical Coordinating Center (CCC). For all changes in scanner and significant scanner upgrades, the investigator will be requested to obtain MRI scans of 3 volunteers acquired prior to changing/upgrading the MRI scanner and the same 3 volunteers again after changing scanners (a total of 6 scans). The site will be allowed to acquire trial subject scans on the new scanner only after obtaining approval of the new or upgraded scanner. Data will be captured in the study database flagging that a major scanner change/upgrade has occurred. However, all primary and secondary analyses will not attempt to adjust for the scanner change.

2. PRIMARY ENDPOINTS

2.1. Brain Parenchymal Fraction (BPF)

Using computerized image analysis software, brain volume loss is detectable at all stages of disease (Miller et al, 2002; Bermel & Bakshi, 2006). Atrophy is an indirect marker of destructive pathologic processes in MS, including the net effects of focal tissue damage in white matter and grey matter, but also diffuse pathologic processes in normal-appearing brain tissue. More than 20 studies show

significant cross-sectional correlations between whole brain atrophy and overall clinical disability (Fisher, 2011a; Fisher, 2011b). Whole brain atrophy (WBA) also correlates with cognitive impairment (Edwards et al, 2001; Rao et al, 1985; Hohol et al, 1997; Benedict et al, 2004; Lazeron et al, 2005), depression (Feinstein et al, 2004), fatigue (Marrie et al, 2005; Tedeschi et al, 2007), and quality of life (Janardhan & Bakshi, 2000; Rudick et al, 2001). Multivariate analysis suggests that disability correlates better with WBA than with lesion measures (Benedict et al, 2004). WBA progresses over the course of MS, with a mean rate in untreated MS patients generally ranging from 0.5-1.5% per year (Fisher, 2011b). Although one small (n=21) early study found atrophy to slow in later disease (Fox et al, 2000), contemporary studies with larger sample sizes (n=69 and n=963) found similar or faster rates of atrophy in PMS compared with RRMS (Fisher et al, 2008; De Stefano et al, 2010). Atrophy progression in PPMS is similar to SPMS (Kalkers et al, 2001). Longitudinal studies found patients with greater rates of atrophy are more likely to worsen clinically (Dastidar et al, 1999; Molyneux et al, 2000; Fisher et al, 2000; Fisher et al, 2002; Dalton et al, 2004; Minneboo et al, 2008; Di Fillippo et al, 2010). For example, a longitudinal study found WBA progression is predictive of cognitive deterioration (Amato et al, 2007). These clinical correlations appear to be stronger later in the disease (i.e., SPMS compared to RRMS – Fisher et al, 2000; Ge et al, 2000). Altogether although additional treatment trial data is needed, face validity, concurrent validity, and predictive validity of WBA in PMS are significant enough to use it as the primary outcome metric in PMS trials. Based on accumulated evidence, an international consensus panel recommended WBA as the primary outcome of phase II PMS trials (Barkhof et al, 2009). Indeed, several recent PMS studies used WBA as the primary outcome, including trials evaluating lamotrigine (Huang et al, 2002) and simvastatin (Chataway et al, 2012). For currently available RRMS therapies, the treatment effects on atrophy range from 30%-50% compared to placebo, including a 34% slowing of atrophy in a phase II trial of Ibudilast in RRMS (Barkhof et al, 2010) and a 49% slowing over 2 years with simvastatin in SPMS (Chataway et al, 2012).

The primary outcome of this trial is WBA, estimated as the change in brain parenchymal fraction (BPF). BPF is a normalized measure of whole brain volume calculated as the volume of brain parenchymal tissue divided by the total volume within a smoothed outer surface of the brain (Rudick et al, 1999). The fully-automated algorithm takes partial volume effects into account, can utilize either FLAIR or dual echo PD-/T2-weighted images, and has a scan-rescan coefficient of variability < 0.2%. Sensitivity analyses for BPF include SIENA and an advanced SIENA technique that utilizes a single longitudinally co-registered image within each patient, which may further reduce variability.

For the purposes of this trial, BPF will be computed based on MRI scans performed at screening, and at weeks 24, 48, 72, and 96. The images will be processed, and reviewed for quality and completeness at the Cleveland Clinic MS MRI Analysis Center. Images will be checked for adherence to protocol, consistency over time, image quality, and completeness of the electronic transfer. This step determines if the MRI data set can be approved for BPF analysis or if it should be rejected, reacquired, or resent from NeuroRx. Once approved, the images will be set up to be analyzed. The image analysis pipeline automatically records numerical results in an internal database. Database records for which the atrophy results have been visually verified will be transmitted to the NeuroNEXT Data Coordinating Center (DCC) in accordance with the procedures outlined in the corresponding data transfer agreement.

2.2. Safety

The primary assessment of safety will compare the percentage of subjects in each group with:

- Treatment-emergent adverse events (TEAEs)
- Treatment-emergent serious adverse events (TESAEs)

For the purposes of this study, a treatment-emergent adverse event (AE) is any untoward medical occurrence in a study subject who was administered a medicinal (investigational) product and which does not necessarily have a causal relationship with this treatment. An AE can therefore be any unfavorable and unintended sign (including a significant abnormal laboratory finding), symptom, or disease temporally associated with the use of a medicinal (investigational) product, whether or not considered related to the medicinal (investigational) product. Adverse events may include the onset of a new illness and the exacerbation of pre-existing conditions. Other untoward events occurring in the framework of a clinical study are also to be recorded as AEs (e.g., those occurring during treatment-free periods, including screening or post-treatment follow-up periods), in association with study-related procedures and assessments or under placebo.

One of the following categories should be selected based on medical judgment, considering the definitions below and all contributing factors:

- **Related**: A clinical event, including laboratory test abnormality, occurs in a plausible time relationship to treatment administration, and which cannot be explained by concurrent disease or other medications or chemicals. The response to withdrawal of the treatment (de-challenge) should be clinically plausible. The event must be definitive pharmacologically or phenomenologically, using a satisfactory re-challenge procedure if necessary.
- **Probably Related**: A clinical event, including laboratory test abnormality, occurs within a reasonable time sequence to administration of the treatment, unlikely to be attributed to concurrent disease or other medications or chemicals, and which follows a clinically reasonable response on withdrawal (dechallenge). Re-challenge information is not required to fulfill this definition.
- **Possibly Related**: A clinical event, including laboratory test abnormality, occurs within a reasonable time sequence to administration of the treatment, but which could also be explained by concurrent disease or other medications or chemicals. Information on treatment withdrawal may be lacking or unclear.
- **Unlikely to be Related**: A clinical event, including laboratory test abnormality, occurs with a temporal relationship to treatment administration that makes a causal relationship improbable, and in which other medications, chemicals, or underlying disease provide plausible explanations.
- **Unrelated**: A clinical event, including laboratory test abnormality, occurs with little or no temporal relationship with treatment administration. May have negative dechallenge and re-challenge information. Typically explained by extraneous factors (e.g., concomitant disease, environmental factors, or other medications or chemicals).

For the purposes of this study, primary interest involves an examination of treatment-related AEs - defined as any AE deemed to be at least possibly related to study treatment. As this is a double-blind study, the causality assessment should be made under the assumption that the subject is receiving

active study medication. If considering unblinding, this assessment should be made prior to unblinding to avoid bias.

An AE is considered serious if it meets one or more of the following criteria:

- Results in death
- Is life-threatening (i.e., a subject is at immediate risk of death at the time of the event, not an event where occurrence in a more severe form might have caused death)
- Requires inpatient hospitalization or prolongation of existing hospitalization
- Results in persistent or significant disability/incapacity
- Results in a congenital anomaly/birth defect
- Is another important medical event

Important medical events that do not result in death, are not life-threatening, or do not require hospitalization may be considered SAEs when, based on appropriate medical judgment, they may jeopardize the subject and may require medical or surgical intervention to prevent one of the outcomes listed above.

[name] will serve as the Medical Safety Monitor (MSM) for this trial. [name] will work closely with the DCC, and will use the online AE reporting system to review all reported SAEs in near real time and evaluate them to identify the need for timely intervention. For any reported SAEs, an automatic email will be sent to [name] to prompt a review of the event for determination of whether the event is unanticipated and/or whether it is related to study drug. With the assistance of the coordinators at the DCC, [name] has the option of requesting additional information about any SAE. He will complete a form for each review, and this information will be entered into the online data entry system.

Thus, in summary, the determination of whether an AE or SAE is treatment-related (at least possibly related to treatment) differs. Because the MSM only reviews SAEs in real-time, the determination of whether or not a non-serious AE is considered treatment-related will be made at the site level. However, for SAEs, the MSM determination of whether or not an SAE is treatment-related will take precedent over the classification at the site level.

2.3. Tolerability

The primary assessment of tolerability will compare the percentage of subjects in each group who:

- Discontinue treatment early (early study termination and/or early study drug withdrawal) due to treatment-emergent AEs or SAEs
- Discontinue treatment early (early study termination and/or early study drug withdrawal) for any reason

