
Reference Therapy, Dosage, and Mode of Administration: Matching-placebo capsules administered orally, twice a day in the morning and evening.

Criteria for Evaluation
 
Primary Safety Endpoints:
 
The proportion of subjects in each group with:
 
 Treatment-emergent adverse events (TEAEs) Treatment-emergent serious adverse events (TESAEs) 
Primary Tolerability Endpoints:
 
The proportion of subjects in each group who:
 
 Discontinue treatment early (early study termination and/or early study drug withdrawal) due to treatment-related AEs or SAEs Discontinue treatment early (early study termination and/or early study drug withdrawal) for any reason 
Primary Activity Endpoint:

Covariate-adjusted mean rate of change in brain atrophy over 96 weeks as measured by brain parenchymal fraction (BPF).

Major Secondary Activity Endpoints:

The secondary endpoints will be measured at 96 weeks by:

- Diffusion tensor imaging (DTI) in descending pyramidal white matter tracts
- Magnetization transfer ratio (MTR) imaging in normal-appearing brain tissue
- Retinal nerve fiber layer as measured by optical coherence tomography (OCT)
- Cortical atrophy as measured by cortical longitudinal atrophy detection algorithm [CLADA]

Additional secondary endpoints to be measured at 96 weeks are:

- Inflammatory disease activity, as measured by T1 lesion volume, T2 lesion volume, and annualized relapse rate
- Disability, as measured by Expanded Disability Status Scale (EDSS) and Multiple Sclerosis Functional Composite (MSFC)
- Quality of Life, as measured by Multiple Sclerosis Impact Scale (MSIS-29), EuroQol 5 Dimensions (EQ-5D), and Short Form-36 Health Survey (SF-36)
- Cognitive impairment, as measured by Symbol Digit Modalities Test and the Selective Reminding Test
- Neuropathic pain, as measured by Brief Pain Inventory (BPI).

Tertiary and Exploratory Endpoints: *see Objectives above.*

Pharmacokinetic: Plasma samples for analysis of ibudilast and its metabolite, 6,7-dihydrodiol (DHD), will be collected and population PK analysis will be performed.

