5.1. Primary Objective

The primary objectives of the study are:

- to evaluate the activity of ibudilast (MN-166) (100 mg/d) versus placebo at 96 weeks as measured by quantitative magnetic resonance imaging (MRI) analysis for whole brain atrophy using brain parenchymal fraction (BPF).
- to evaluate the safety and tolerability of ibudilast (MN-166) (100 mg/d) versus placebo administered orally in subjects with primary and secondary progressive multiple sclerosis.

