9.6. Study Drug Accountability

Investigational clinical supplies must be received by the CSSPI or a designated person at the study site, handled and stored safely and properly, and kept in a secured location to which only the Investigator and/or designated assistants have access. Clinical supplies are to be dispensed only in accordance with the protocol.

The CSSPI or designee is responsible for keeping accurate records of the clinical supplies received from the Sponsor or designee, the amount dispensed to and returned by the subjects, and the amount remaining at the conclusion of the study. At the end of the study, all clinical supplies must be returned to the Sponsor, or designee, after confirmation with the CRA (Clinical Research Associate) or destroyed at the clinical site. Study drug will not be destroyed until written documentation is received from the study sponsor or designee. Proper documentation of the destruction of study drug must be provided by the site.

The following information is to be included in the CRF: visit medication dispensed, dosing start/stop dates, dosage level achieved (60 – 100 mg/d) number of capsules dispensed and number of capsules returned.

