$$[a_{ih} \ b_{ih}]^T \sim \mathcal{N}(\mathbf{0}, \mathbf{G}), [a_h \ b_h \ c_h \ d_h]^T \sim \mathcal{N}(\mathbf{0}, \mathbf{H}), \epsilon_{ij} \sim \mathcal{N}(0, \sigma^2 \mathbf{I}_i), \text{ and } [a_i \ b_i]^T \perp [a_h \ b_h \ c_h \ d_h]^T \perp \epsilon_{ij}.$$

If individual site variance components in \mathbf{H} are negligible, then the associated random effects will be omitted to simplify the model. In the case that all \mathbf{H} components are negligible, we will revert to Equation (1) for the analysis.

Primary Objective #2: To evaluate the safety and tolerability of ibudilast versus placebo.

The main assessment of safety will involve a comparison of treatment-related SAEs across the two treatment groups. This will be assessed in two ways. First, the percentage of subjects who experience any treatment-related SAE in each group will be compared using a chi-square test. Then, the rates of treatment-related SAEs in each group will be compared using a Poisson regression model. We will also assess the values of laboratory assessments over time across the two groups using a LMM. To assess tolerability, the percentage of subjects who complete the entire treatment period will be compared across the two groups using a chi-square test. Appropriate constraints for baseline imbalance will be used in all statistical models.

Major Secondary Objectives: *To evaluate the activity of ibudilast at two years versus placebo, as measured by:*

- (1) *Diffusion tensor imaging (DTI) in descending pyramidal white matter tracts*
- (2) *Magnetization transfer ratio (MTR) imaging in normal-appearing brain tissue*
- (3) *Retinal nerve fiber thickness as measured by optical coherence tomography (OCT)*
- (4) *Cortical atrophy as measured by cortical longitudinal atrophy detection algorithm (CLADA)*

The secondary objectives will be analyzed using a model similar to that described above for the assessment of BPF. An exception is the OCT analysis will require additional random effects for eyes nested within patients. Additional details are provided below. The baseline intercepts will again be constrained to be equal to account for baseline imbalance.

Other Objectives

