7.2.2 Tolerability

The assessment of tolerability will involve assessing the percentage of subjects in each group who:

- Discontinue treatment early (early study termination and/or early study drug withdrawal) due to treatment-emergent AEs or SAEs
- Discontinue treatment early (early study termination and/or early study drug withdrawal) for any reason

Both will be assessed using a model similar to that described in [section 7.2.1](#) for the assessment of treatment-related AEs and SAEs.

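### The primary tolerability endpoints count only early discontinuation, so no planned tolerability analysis shows how many subjects stayed on the 100 mg/d named in the protocol's objective

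*Combined protocol and SAP*

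**What the plan says.** The objective names a dose. Protocol 5.1, like the Synopsis, sets out "to evaluate the safety and tolerability of ibudilast (MN-166) (100 mg/d) versus placebo administered orally". SAP 1.1 restates this objective without a dose, but SAP Section 1 labels the active arm 100 mg/day.

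The regimen is adjustable. Under SAP Section 1, subjects with intolerable side effects after Day 15 "may reduce their dose to either 4 capsules twice a day (80 mg/day for those taking MN-166) or 3 capsules" twice a day. Those with intolerable effects at Day 14 may stay on the starting 3 capsules twice a day. The daily dose can move among these levels during the first 8 weeks and must then be held (also Protocol 6.1.2). Splitting the same daily dose into three administrations is a separate option.

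The tolerability measures concern stopping or completing:

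- SAP 2.3, first endpoint: "Discontinue treatment early (early study termination and/or early study drug withdrawal) due to treatment-emergent AEs or SAEs".
- SAP 2.3, second endpoint: "Discontinue treatment early (early study termination and/or early study drug withdrawal) for any reason".
- SAP 7.2.2 repeats both: "The assessment of tolerability will involve assessing the percentage of subjects in each group who" discontinue on these two definitions, analysed with the logistic model of 7.2.1.
- Protocol Synopsis, Criteria for Evaluation: the same pair, except that the first reads "Discontinue treatment early (early study termination and/or early study drug withdrawal) due to treatment-related AEs or SAEs".
- Protocol 12.1.2: "To assess tolerability, the percentage of subjects who complete the entire treatment period will be compared across the two groups".

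The dose reached is collected. Protocol 9.6 lists among the CRF items "dosage level achieved (60 – 100 mg/d) number of capsules dispensed".

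**The concern.** Stepping down is one of the plan's own responses to intolerance, and a subject still on a reduced dose at Week 8 stays on it for the remaining 88 weeks. Someone who cannot take 100 mg/d in week 3 and completes 96 weeks on 60 mg/d has neither discontinued nor failed to complete. Every tolerability measure listed above therefore records a non-event.

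The endpoints thus describe how many subjects stay on some permitted dose between 60 and 100 mg/d. That is a reasonable question, but it is not the one in Protocol 5.1. If the results are reported under that objective, a similar discontinuation rate in the two arms could be presented as a finding about 100 mg/d with no figure showing how many subjects remained on it. A reader choosing a dose for the next trial would need that figure.

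**Working it through.** **Step 1. Follow a step-down subject through each planned measure.** Take a subject who reduces to 6 capsules a day for nausea in week 3 and completes Week 96.

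| Measure | Result for this subject |
|---|---|
| Discontinued because of AEs (SAP 2.3, 7.2.2; Protocol Synopsis) | non-event |
| Discontinued for any reason (same places) | non-event |
| Completed treatment (Protocol 12.1.2) | completer |
| Any treatment-related AE (SAP 7.2.1) | event, if the nausea is judged at least possibly related |
| Dose level by arm | not planned |

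The per-protocol set does not fill the gap, because SAP 6.1.2 applies it to efficacy only. The exploratory population PK work will involve dose, but it is not a tolerability analysis.

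**Step 2. Reproduce the plan's power statement.** SAP 9.2 claims at least 80% power for a 15-point difference in safety or tolerability. Inputs: n = 125 per arm (SAP 1), alpha 0.10 (SAP 9.2), two-sided (the alternative in SAP 7.2.1). A two-proportion test stands in for the logistic model:

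power = Φ{ [ |p1 − p2| − 1.645 × √(2 p̄(1 − p̄)/n) ] / √[ (p1(1 − p1) + p2(1 − p2))/n ] }, with p̄ the mean of p1 and p2.

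For 15% versus 30%, p̄ = 0.225. The null standard error is √(2 × 0.225 × 0.775/125) = 0.0528, and 1.645 × 0.0528 = 0.0869. The alternative standard error is √((0.1275 + 0.2100)/125) = 0.0520. Then (0.15 − 0.0869)/0.0520 = 1.21, giving power 0.888.

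Other 15-point pairs: 10% v 25%, 0.934; 20% v 35%, 0.847; 25% v 40%, 0.816; 30% v 45%, 0.792; minimum 0.769 at 42.5% v 57.5%. The documents support low base rates: 10% assumed dropout (SAP 9.1), and 100% − 86% = 14% non-completion at 60 mg/d in the earlier MS trial (Protocol 4.6.3). At such rates the statement reproduces, so the power figure is not the problem.

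**Step 3. Illustrate what the endpoint can miss.** The documents give no dose-reduction rate, so every rate below is assumed. Each pair is placebo / ibudilast. Combined = discontinued + reduced, with no subject counted twice.

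| Discontinued | Reduced | Discontinuation difference (power) | Combined | Combined difference (power) |
|---|---|---|---|---|
| 10% / 10% | 5% / 5% | 0 points (0.10) | 15% / 15% | 0 points (0.10) |
| 10% / 10% | 5% / 15% | 0 points (0.10) | 15% / 25% | 10 points (0.631) |
| 10% / 10% | 5% / 20% | 0 points (0.10) | 15% / 30% | 15 points (0.888) |
| 10% / 10% | 5% / 25% | 0 points (0.10) | 15% / 35% | 20 points (0.980) |
| 15% / 15% | 5% / 20% | 0 points (0.10) | 20% / 35% | 15 points (0.847) |
| 10% / 15% | 5% / 15% | 5 points (0.326) | 15% / 30% | 15 points (0.888) |

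With no true difference the rejection rate is simply alpha, 0.10. The first row matters as much as the others: if reductions are equally common in both arms, nothing is lost.

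**Step 4. What the documents' own data show.** Protocol 4.6.5 gives a case where stopping and symptoms diverge. In the medication-overuse-headache study at 80 mg/d, nausea or GI upset occurred in 10/15 on ibudilast versus 2/19 on placebo, while withdrawals were 2/15 versus 2/19 and neither ibudilast withdrawal was attributed to GI symptoms. The same section also points the other way: 4/11 versus 4/11 in the phase 1 methamphetamine crossover study at 100 mg/d, and nausea in 0/9 healthy volunteers and 1/9 diabetic subjects in the 80-100 mg/d repeat-dose study. These are adverse-event counts. They make a gap plausible but do not estimate a reduction rate.

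**The case against.** The strongest reply is that the intolerance is not lost. SAP 7.2.1 treats the comparison of treatment-related AEs and SAEs as its principal look at safety and tolerability. It covers percentages overall and by organ class, with preferred terms examined where a class differs, and also event rates. Protocol 11.1 adds a clinical and statistical review of AEs. A reader might infer that a subject who steps down disappears from the results; the documents do not support that. What remains of the concern is narrower. The any-AE model counts brief mild nausea the same as nausea that ended full dosing for good, and it cannot say what share stayed on 10 capsules a day.

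Second, a reader might infer that the plan declares step-down subjects to have tolerated 100 mg/d. No document says so. SAP 1.1 names no dose, and the Synopsis describes the product as given up to 100 mg/d. Comparing arms as randomised under a flexible regimen is a legitimate choice. That stands, and it makes the remedy partly one of labelling. But Protocol 5.1 and the Synopsis do name 100 mg/d, so the label and the endpoint still disagree.

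Third, the window is limited. Daily dose may change only in the first 8 weeks, so later intolerance should appear mainly as discontinuation. That is true, but a reduction still in place at Week 8 is fixed for the rest of treatment.

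Fourth, the prior AE data are mixed, and in the headache study the nausea was mostly mild and subjects were titrated back up. That also stands, and it is why no size is claimed.

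**Conclusion.** The point holds as a mismatch between the protocol's stated objective and what its tolerability endpoints measure. The endpoints measure persistence on a flexible 60-100 mg/d regimen. No planned tolerability analysis shows the proportion remaining on the full regimen, although the data are collected.

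Its size cannot be stated. With equal discontinuation in the two arms, the assumed scenarios give an unseen difference of 0 to 20 points. The 35% versus 20% contrast is one of those assumptions, not a forecast. A reader might infer that a large share of the ibudilast arm will be unable to take 100 mg/d; the documents contain no reduction rate to support that.

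Nor does the point require a third primary test. Several safety and tolerability comparisons already run at 0.10, and a supportive analysis answers the question. It is a cheap improvement worth making. It does not show the existing endpoints to be invalid.

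**What to change.** In SAP 2.3 and 7.2.2, with matching text in the Protocol Synopsis (Criteria for Evaluation) and Protocol 12.1.2:

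1. Add a prespecified supportive comparison, using the SAP 7.2.1 logistic model and the SAP 6.2 population. The outcome is the proportion in each arm who discontinue study drug early, or whose assigned daily regimen at the end of Week 8 is below 10 capsules. Placebo subjects follow the same capsule steps, so the comparison stays randomised and blinded.
2. State what is not a reduction: a temporary laboratory-driven interruption under Protocol 8.6.2, and three-times-daily splitting of the full daily dose.
3. Tabulate 6, 8 and 10 capsules per day by arm at Week 8 and Week 96.
4. Describe the discontinuation-only endpoints as tolerability of the flexible 60-100 mg/d regimen, and rest any statement about 100 mg/d itself on the supportive comparison.
5. While editing, reconcile the first endpoint, which is limited to treatment-related events in the Synopsis but uses treatment-emergent events in the SAP.

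No dosing rule changes and no new data are needed. The cost is one extra model, one table and some wording. The downside is that the tolerability result may look less favourable.
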